1.4.2 Potential Benefits

The benefits include the potential of decreasing the participant's reactivity to peanuts after an accidental ingestion and the altering of the natural progression of peanut allergy by inducing peanut tolerance. The subject may potentially become clinically and immunologically tolerant to peanut, which otherwise occurs in only about 20% of children. A major obstacle to the widespread implementation of current treatment strategies is the requirement for daily dosing. This outcome may provide new evidence that daily treatment is not required for an indefinite period to maintain a state of desensitization.

In this way, this study will also help expand the knowledge of food allergy in general and may lead to new management and therapeutic protocols for individuals with food allergies.

2. OBJECTIVES

2.1 PRIMARY OBJECTIVE

The primary objective is to determine whether 134 weeks of peanut OIT induces desensitization in children with peanut allergy.

2.2 SECONDARY OBJECTIVES

1. To determine whether 134 weeks of peanut OIT induces tolerance in children with peanut allergy.
2. To assess the safety of peanut OIT and subsequent withdrawal of OIT in this population.
3. To define the immunological responses underlying desensitization and tolerance to peanut.

3. STUDY DESIGN

3.1 DESCRIPTION

This is a randomized, double-blind, placebo-controlled, multi-center study comparing peanut oral immunotherapy to placebo.

Eligible participants with peanut allergy will be randomly assigned to receive either peanut OIT or placebo for 134 weeks followed by peanut avoidance for 26 weeks.

An initial blinded oral food challenge (OFC) to 1 g of peanut flour (500 mg peanut protein) will be conducted. Participants must have a clinical reaction during this blinded OFC to initiate study dosing. After the initial blinded OFC, the study design includes the following:

Initial Dose Escalation: This will occur on a single day in which multiple doses are given. Peanut or placebo dosing will be given incrementally and increase every 15-30 minutes until a dose of 12 mg peanut flour (6 mg peanut protein) or placebo flour is given. The first four doses will be administered as a peanut flour extract of 0.1 to 0.8 mg peanut protein, which is 10 to 80 microliters peanut flour extract, or placebo flour extract. The last three doses will be given as peanut flour of 3 to 12 mg peanut flour (1.5 to 6 mg peanut protein) or placebo flour. Participants must tolerate a dose of at least 3 mg peanut flour (1.5 mg peanut protein) or placebo flour to remain in the study.

Build-up: After the initial dose escalation day, the participant will return to the research unit the next morning for an observed dose administration of the highest tolerated dose from the initial escalation day. The participant will then continue on the daily OIT dosing at home and return to the research unit every 2 weeks for a dose escalation. The dosing escalations will be consistent with previous similar OIT studies. The dosing escalation table is as below. Participants who do not reach the 4000 mg peanut flour (2000 mg peanut protein) or placebo flour dose during the Build-up phase may enter maintenance phase at their highest tolerated dose, which must be at least 500 mg peanut flour (250 mg peanut protein) or placebo flour.

The build-up phase will comprise 30 weeks.

Maintenance: The participant will continue on daily OIT with return visits every 13 weeks. At the end of this phase the participant will undergo a blinded OFC to 10 g peanut flour (5 g peanut protein).

The maintenance phase will comprise 104 weeks.

Avoidance: In this phase participants will stop OIT and will avoid peanut consumption. They will be seen 2 weeks and 26 weeks after initiating this phase. At the completion of this phase participants will have a blinded OFC to 10 g peanut flour (5 g peanut protein). Participants who do not have a clinical reaction to the blinded OFC will undergo an Open Food Challenge (OpFC) (See [Section 6.4.1.3](#)).

The avoidance phase will comprise 26 weeks.

Post-challenge: If participants do not have a clinical reaction during the OpFC at the end of avoidance, they will be allowed to consume peanut and will have one visit which will include peripheral blood sampling for mechanistic assays assessments.

The post-challenge phase will comprise 2 weeks.

	Dose Escalation for Maximum Initial Dose Escalation of:			First day at Dose	Week Number
	6 mg¹	3 mg	1.5 mg		
Initial Dose Escalation	0.1 ²	0.1 ²	0.1 ²	0	0
	0.2	0.2	0.2	0	0
	0.4	0.4	0.4	0	0
	0.8	0.8	0.8	0	0
	1.5 ³	1.5 ³	1.5 ³	0	0
	3.0	3.0		0	0
	6.0			0	0
Build-up	6.0	3.0	1.5	1	0
	12	6.0	3.0	14	2
	25	12	6.0	28	4
	50	25	12	42	6
	100	50	25	56	8
	150	100	50	70	10
	250	150	100	84	12
	400	250	150	98	14
	600	400	250	112	16
	900	600	400	126	18
	1200	900	600	140	20
	1600	1200	900	154	22
	2000	1600	1200	168	24
	2000	2000	1600	182	26
2000	2000	2000	196	28	
Maintenance	2000	2000	2000	210	30
Avoidance	0	0	0	938	134
Post-challenge	0	0	0	1120	160

Table 1 Screening, Initial Dose Escalation, Build-up, Maintenance, Avoidance and Post-Challenge

¹ Amounts expressed in mg peanut protein

² Peanut flour extract (0.1 to 0.8 mg doses)

³ Peanut flour (1.5 to 6.0 mg doses)

[figure not shown]

Figure 1 Screening, Initial Dose Escalation, Build-up, Maintenance, Avoidance and Post-Challenge
 *Amounts expressed in mg of peanut protein

3.2 STUDY DURATION

Total study duration will be up to 238 weeks (slightly more than 4 and one-half years).

- Enrollment will be up to 78 weeks.
- Study participation will be 162 weeks, which includes the initial dose escalation, build-up, maintenance, avoidance, and post-challenge.

3.3 STUDY ENDPOINTS

3.3.1 Primary Endpoint

The primary endpoint is the proportion of participants desensitized to peanut after 134 weeks OIT.

Participants who pass a blinded OFC to 10 g of peanut flour (5 g of peanut protein) at this time without significant symptoms as described in [Section 6.4.3](#) will be considered desensitized to peanut. Failure will be defined as either unable to undergo the final food challenge or inability to tolerate the maximum dose because of significant symptoms such as hives, wheezing, vomiting, or laryngeal edema.

3.3.2 Secondary Endpoints

Efficacy:

1. Tolerance Endpoint
The proportion of participants who pass both the blinded OFC to 10 g peanut flour (5 g peanut protein) and the Open OFC to 8 g peanut protein in natural food form at week 160.
Passing a blinded OFC is defined in [Section 3.3.1](#).
Passing an Open OFC is defined in Section 6.4.3.
2. Transient Desensitization Endpoint
This is the change in proportion of participants who pass the blinded OFC to 10 g peanut flour (5 g peanut protein) at week 134 and week 160.
Passing a blinded OFC is defined in [Section 3.3.1](#).
3. Highest Tolerated Cumulative Dose Endpoint
The highest tolerated cumulative dose of peanut protein during the blinded OFCs will also be collected and analyzed.

Safety:

1. The incidence of all adverse events.
2. Rates of withdrawal from OIT or placebo.

Mechanistic:

Changes in the following markers of immune mediation:

1. Secreted cytokines
2. Anti-peanut IgE, IgG, IgG4 and secretory IgA
3. Epitope arrays
4. IgE-facilitated, CD23-dependent allergen binding to B cells
5. Serum, stools, and saliva assays
6. PBMC expression of transcription factors and cytokines relevant to food allergy

7. CD4+ CD25+ FoxP3+ Tregs
8. DNA-HLA genotyping
9. Peanut-specific T cells
10. Ara h 1 and Ara h 2 reactive T cells
11. Th2A Subset Analysis Basophil activation
12. B cells

3.4 PREMATURE TERMINATION OR SUSPENSION OF THE TRIAL

3.4.1 Stopping Rules

If any of the stopping rules listed below are met, study enrollment will be suspended, the initial dose escalation days will be suspended, dose escalation during Build-up will be stopped, and all enrolled participants will remain on their current dose pending expedited review of all pertinent data by the Data Safety Monitoring Board:

- Any death related to peanut OIT dosing
- More than one event comprising systemic allergic symptoms with significant hypotension at any stage of the protocol
- More than 3 participants require more than 2 injections of epinephrine during dosing of the peanut product
- More than 3 of the following events:
 - Severe adverse event, other than anaphylaxis, related to investigational product
 - Eosinophilic esophagitis

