Oral food challenges may induce an allergic response. Three OFCs will be conducted: one at study entry, one at the end of therapy, and one 26 weeks after cessation of therapy. Allergic reactions can be severe and include life-threatening allergic reactions; however, the risk of an allergic reaction is reduced by initiating the challenge with a very small amount of the food, gradually increasing the dose, and stopping the challenge at the first sign of a reaction. If participants have an allergic reaction during the challenges, they may need oral, intramuscular, or intravenous medications (participants judged by the investigator to be at significant risk of severe reaction will have an IV catheter placed before the OFCs). Trained personnel, including a physician, as well as medications and equipment, will be immediately available to treat any reaction. The DBPCFCs will potentially be made safer by using orally ingested foods with masking agents instead of encapsulated peanut powder, thereby allowing for earlier detection of allergic reactions based on oral symptoms that would be missed with the use of capsules.³⁰ It should be noted that life-threatening anaphylaxis is a known but rare

complication of oral food challenge among the investigators who are participating in this protocol. To date, there have been no deaths from oral food challenge among these investigators.³¹

The risks of skin prick testing are small. Skin prick testing may result in a small, pruritic hive where the test is placed. Usually, the hives resolve within 1-2 hours, but rarely a subject may have local swelling that takes two to three days to clear entirely. In approximately 1 out of 10,000 tests the subject may experience other allergic symptoms including sneezing, ocular pruritus and tearing, rhinorrhea, and/or urticaria. Very rarely, some individuals with these types of symptoms may develop a serious allergic reaction that is life threatening, but no deaths from skin prick testing using standard dosing techniques have been reported in fifty years.

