5.2 DISCONTINUATION OF STUDY TREATMENT

Participants will be terminated from further allergen therapy for the following reasons:

- Severe anaphylaxis with hypotension secondary to OIT dosing or any peanut food challenge.
- Inability to reach 3 mg peanut flour (1.5 mg peanut protein) during the initial dose escalation.
- Inability to reach 500 mg (250 mg peanut protein) during the Build-up phase.
- Poor control or persistent activation of secondary atopic disease (e.g., AD, asthma).
- Development of eosinophilic gastrointestinal disease.
- Circumstances (e.g., concurrent illness, such as gastroenteritis) requiring missed home dosing of > 14 consecutive days.
- Non-adherence with home dosing protocol with excessive missed days, defined as 3 occasions on which more than 3 consecutive home doses of study medication are missed.
- Eosinophilic esophagitis.
- Severe adverse event other than anaphylaxis related to investigational product.

Further care will be provided according to the judgment and practice of the site investigator.

Any subject deemed to have severe symptoms and who receives aggressive therapy at any time per investigator's discretion, should be discontinued from further escalation and followed-up as appropriate.

Participants who cease therapy should be asked to complete all assessments listed for Discontinuation Visit in Appendix 2.

If study treatment is discontinued, the DAIT/NIAID Medical Monitor will be notified.

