8.2.2 Study Specific Adverse Events

During the study it is anticipated that participants undergoing study procedures involving administration of peanut flour (blinded OFC, IDE, home or clinic OIT/placebo dosing) will experience allergic symptoms related to peanut allergy. Events related to these study procedures will be captured on procedure-specific forms, and will NOT be recorded as adverse events, unless they meet certain criteria as defined in [Section 8.3.2.2](#).

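### The single-death trigger in Section 3.4.1 is limited to OIT dosing, so a first, isolated fatal reaction to a study food challenge does not by itself meet any stopping rule

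*Combined protocol and SAP*

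**What the plan says.** Section 3.4.1 has four triggers. Meeting any one suspends enrollment and initial dose escalation, stops build-up escalation and holds everyone at their current dose, "pending expedited review of all pertinent data by the Data Safety Monitoring Board". The triggers are:

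- Death: "Any death related to peanut OIT dosing".
- Hypotension: "More than one event comprising systemic allergic symptoms with significant hypotension at any stage of the protocol".
- Epinephrine: "More than 3 participants require more than 2 injections of epinephrine during dosing of the peanut product".
- More than three events in a class made up of eosinophilic esophagitis and "Severe adverse event, other than anaphylaxis, related to investigational product".

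The protocol gives peanut by daily dosing and also by challenge: a blinded 500 mg challenge at screening, blinded 5 g challenges at weeks 134 and 160, and an open challenge for those who pass at week 160. Section 1.4.1 says of the challenges: "Allergic reactions can be severe and include life-threatening allergic reactions".

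Two other sections list dosing and challenges as different things. Section 5.2, on stopping treatment in an individual, has "Severe anaphylaxis with hypotension secondary to OIT dosing or any peanut food challenge". Section 8.2.2 lists procedures involving "administration of peanut flour (blinded OFC, IDE, home or clinic OIT/placebo dosing". Section 8.3.2.2 uses a wider notion, administration of investigational product or placebo, and puts the blinded challenge inside it. The death bullet does not use that wider term.

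**The concern.** The death bullet is the only one of the four that a single event can meet, and it is tied to one of the two ways in which the protocol gives peanut. The bullet next to it has no such limit. Two non-fatal hypotensive reactions during challenges would therefore force the suspension and the expedited review, while one death during a challenge would not. The documents give no reason for the difference.

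At stake is whether the response to the gravest possible outcome of a study procedure is fixed in advance or left to judgment at the time. The screening challenge is where this matters most, because it is repeated in new children for as long as enrollment is open.

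**Working it through.** The plan gives no figure to reproduce. The check applies each trigger in Section 3.4.1, with its own count and scope, to one fatal reaction during a study challenge.

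| Trigger | Count needed | What one fatal challenge reaction adds | Met by it alone? |
|---|---|---|---|
| Death | 1 | 0: a challenge is not OIT dosing | No |
| Hypotension | at least 2 | 1 with significant hypotension, 0 without (for example, purely respiratory) | No |
| Epinephrine | at least 4 participants | at most 1, and only if a challenge counts as dosing of the product, which is not stated | No |
| Severe event or eosinophilic esophagitis | at least 4 | 0 if anaphylaxis, at most 1 otherwise | No |

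Result for a first, isolated event: 0 of 4 triggers met. With one earlier hypotensive systemic reaction anywhere in the trial, a fatal reaction with hypotension makes the count 1 + 1 = 2, and the hypotension trigger is met. The epinephrine trigger could be met only if three participants had already qualified.

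**Can the death bullet be read to include challenges?** At screening the child has had no OIT, and placebo children never receive peanut OIT. A challenge death in either group cannot be tied to peanut OIT dosing without setting aside the distinction in Sections 5.2 and 8.2.2.

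**How many screening challenges?** Section 9.3 plans 144 participants. Section 4.1 requires each to be at least 12 and under 48 months old and to react at the screening challenge. That gives at least 144 challenges in reactive children, plus those in children who do not react and are not enrolled.

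**What could the suspensions still act on when the 5 g challenges begin?**

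- Enrollment lasts up to 78 weeks (Section 3.2) and build-up up to 45 weeks (Section 6.1.1). Last build-up ends by 78 + 45 = week 123 of the trial.
- The first 5 g challenge is scheduled at week 134, day 938.
- Earliest case under the Section 6.1.1 windows: visits 2 to 16 are 15 visits, each up to 3 days early, so 15 × 3 = 45 days; visit 24 may be a further 3 days early. Day 938 − 45 − 3 = 890, and 890 / 7 = 127.1 weeks.
- Margin: 127.1 − 123 = about 4 weeks in the earliest case, 134 − 123 = 11 weeks as scheduled.

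This assumes that the trial clock starts at the first child's visit 0, that the 78 weeks run to the last child's visit 0, and that enrollment does not overrun. On that basis enrollment, initial escalation and build-up are over before any 5 g challenge. Section 3.4.1 does not list the challenges themselves among the suspended activities.

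**The case against.** The strongest reply is that the safety system does not depend on Section 3.4.1 alone. A death is a serious adverse event (Section 8.2.4), reported to the sponsor within 24 hours (Section 8.5.1). For serious systemic reactions to peanut flour or placebo administration, the Medical Monitor, the Protocol Chair or co-Chair and the trial physician are notified within 24 hours and decide whether expedited reporting and the stopping rules apply (Section 8.3.2.3). A fatal, unexpected suspected reaction goes to the FDA within 7 calendar days (Section 8.5.2), and events reported there also go to the board on an expedited basis (Section 8.5.3). Section 1.4.1 reports no challenge deaths among these investigators, so a fatal outcome could well be classed as unexpected. The board may recommend terminating the study (Section 8.1).

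Most of this stands. A reader might infer that the board would not hear of a challenge death, or that enrollment must carry on after one. The documents support neither: the listed triggers do not bar a discretionary halt. But the expedited route depends on how the event is classified or on the Medical Monitor's decision, and it carries no automatic pause. Officials who checked the event against Section 3.4.1 as written would find no rule met.

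A second reply is that the vocabulary is loose. Section 8.3.2.2 records challenge symptoms on forms it calls dosing-specific, Section 5.2 serves a different purpose, and different scopes in different bullets are not in themselves a contradiction. This is fair. It shows that the scope is unclear and that no deliberate exclusion can be inferred. It does not show that challenges are covered.

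**Conclusion.** The point holds for a first, isolated event: one fatal reaction to a study challenge meets 0 of the 4 triggers and only adds to the multi-event counts.

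Two stronger readings are tempting and do not hold. One is that no challenge death could ever trigger Section 3.4.1. The hypotension trigger applies throughout the protocol, so a fatal reaction with significant hypotension that follows an earlier qualifying event does trigger it. The other is that every study challenge is exposed to a missing pause. With 15% dropout there would be about 144 × 2 × 0.85 = 245 blinded 5 g challenges, but on the planned timeline they come after the activities that the rule suspends. For those, and for the open challenge, the main loss is the assured expedited review.

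The full gap, suspension and review together, therefore concerns the screening challenges, at least 144 of them. It is assumed here that suspending enrollment would also stop new screening challenges; Section 3.4.1 does not say so in terms.

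The documents give no probability for such a death. No endpoint, estimate or power figure is affected. It is a safety-relevant ambiguity in one bullet, and the sponsor should correct it because doing so costs almost nothing.

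**What to change.** The sponsor should reconcile the scope terms in Sections 3.4.1, 5.2, 8.2.2 and 8.3.2.2, so that the death bullet states explicitly whether study peanut challenges are covered: screening, 5 g and open. The open challenge needs its own mention because the lists in Sections 8.2.2 and 8.3.2.2 name only the blinded ones. The result should be consistent with the scope of the hypotension bullet. It would also help to say whether the epinephrine bullet counts challenges as dosing. No particular clinical rule or threshold is proposed here; that choice belongs to the sponsor and the monitoring board.

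The cost is a wording change to one bullet (a second if the epinephrine bullet is clarified too), made by protocol amendment. It uses the existing board and adds no procedures. The change to the death bullet has no effect on the trial unless such a death occurs.

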8.3.2.2 Adverse Events Occurring During Peanut Flour / Placebo Administration

Guidelines for recording events that occur during investigational product or placebo administration, which include blinded OFC, IDE and daily home and clinic dosing:

All symptoms or events that occur within two hours and that are expected according to the General Investigational Plan and related to administration of investigational product or placebo will be recorded on the dosing-specific CRFs for blinded OFC, IDE, home or clinic dosing. They will be graded according to table 3 ([Section 8.4](#)).

Any of the following symptoms or events that occur at any time related to dosing, should also be recorded as an adverse event:

- hypotension
- cyanosis
- SpO₂ < 92%
- confusion
- collapse
- loss of consciousness

- incontinence
- required more than 2 injections of epinephrine

Any such symptom or event that meets the serious criteria in [Section 8.2.4](#) will also be reported as an SAE.

Any symptom or event that occurs more than two hours after dosing will be recorded as an adverse event.

Any symptom or event that is not expected according to the General Investigational Plan will be recorded as an adverse event.

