8.4 GRADING AND ATTRIBUTION OF ADVERSE EVENTS

8.4.1 Grading Criteria

8.4.1.1 Adverse Events Related to Study Procedures

Symptoms associated with systemic allergic reactions and/or anaphylaxis that occur during administration of peanut flour or placebo will be graded according to Table 3 below.

All AEs will be collected and recorded in the source documents from visit -1 until the time the participant completes the study (visit 27), or prematurely withdraws from the study. Table 3 was adapted from the grading of allergic reactions in the Consortium of Food Allergy Research (CoFAR3) protocol, entitled “Oral Desensitization to Egg with Subsequent Induction of Tolerance for Egg-Allergic Children”. CoFAR3 protocol is conducted under the IND #13239 sponsored by the DAIT/NIAID. This completed study assessed the oral desensitization to egg and induction of tolerance in egg-allergic children between the ages of 5 and 18 years (ClinicalTrials.gov Identifier: NCT00461097).

Table 3 Grading of Symptoms and Events Related to Peanut Flour Administration

Grade	1 (Mild)	2 (Moderate)	3 (Severe)	4 (Life threatening)
General	Transient or mild discomforts (< 48 hours)	Symptoms that produce mild to moderate limitation in activity some assistance may be needed	Marked limitation in activity, some assistance usually required Medical intervention; hospitalization is possible	Extreme limitation in activity, significant assistance required; Intervention is required; hospitalization is probable

Cardio-vascular			Hypotension Change in mental status	Persistent hypotension and/or hypoxia with resultant decreased level of consciousness associated with collapse and/or incontinence or other life threatening symptoms.
Skin	Skin flushing or pruritus, limited localized hives, swelling or rash	Persistent systemic hives, swelling		
Respiratory	Transient symptoms such as rhinorrhea, sneezing, nasal congestion, throat discomfort, and occasional cough	Wheezing without dyspnea, persistent cough	Bronchospasm, wheezing with dyspnea Laryngeal edema Throat tightness with hoarseness	
Gastro-intestinal	Abdominal discomfort, minor episode of vomiting	Persistent moderate abdominal pain, cramping, nausea Increased vomiting or other symptoms such as throat tightness without vomiting	Significant abdominal pain, cramping Repetitive vomiting	

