Appendix 3: Anaphylaxis Staging System

Anaphylaxis is a generalized allergic reaction that is rapid in onset and may progress to death.⁴⁰

Criteria for Diagnosis

Anaphylaxis is likely when any *one* of the three following sets of criteria are fulfilled:

1. Acute onset of an illness (minutes to hours) with involvement of:
 - Skin/mucosal tissue (e.g., *generalized* hives, itch or flush, swollen lips/tongue/uvula)
AND
 - Airway compromise (e.g., dyspnea, stridor, wheeze/ bronchospasm, hypoxia, reduced PEF) *AND/OR*
 - Reduced BP or associated symptoms (e.g., hypotonia, syncope, incontinence)
2. Two or more of the following that occur rapidly after exposure to the allergen (minutes to hours):
 - Skin/mucosal tissue (e.g., *generalized* hives, itch/flush, swollen lips/tongue/uvula)**
 - Airway compromise (e.g., dyspnea, stridor wheeze/bronchospasm, hypoxia, reduced PEF)
 - Reduced BP or associated symptoms (e.g., hypotonia, syncope, incontinence)
 - *Persistent* GI symptoms (e.g., nausea, vomiting, crampy abdominal pain)
3. Reduced BP after exposure to the allergen (minutes to hours):
 - Infants and Children: low systolic BP (age-specific) or > 30% drop in systolic BP*
 - Adults: systolic BP < 90 mm Hg or > 30% drop from their baseline

* Low systolic BP for children is defined as < 70 mmHg from 1 month to 1 year; less than (70 mmHg + [2 x age]) from 1-10 years; and < 90 mmHg from age 11-17 years.

** Isolated skin or mucosal lesions following the ingestion of a food constitute a “food-induced allergic reaction.”

Staging System of Severity of Anaphylaxis

Stage Defined By

1. *Mild (skin & subcutaneous tissues, GI, &/or mild respiratory)*
Flushing, urticaria, periorbital or facial angioedema; mild dyspnea, wheeze or upper respiratory symptoms; mild abdominal pain and/or emesis
2. *Moderate (mild symptoms + features suggesting moderate respiratory, cardiovascular or GI symptoms)*
Marked dysphagia, hoarseness, and/or stridor; shortness of breath, wheezing and retractions; crampy abdominal pain, recurrent vomiting and/or diarrhea; and/or mild dizziness
3. *Severe (hypoxia, hypotension, or neurological compromise)*
Cyanosis or SpO₂ < 92% at any stage, hypotension, confusion, collapse, loss of consciousness; or incontinence.

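### The stopping rules give no automatic pause for non-fatal severe anaphylaxis that arises through hypoxia or neurological compromise, without hypotension, and is treated with one or two epinephrine injections

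*Combined protocol and SAP*

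**What the plan says.** Section 3.4.1 lists four triggers. Any one of them suspends enrollment and initial dose escalation, stops escalation in build-up and holds current doses pending expedited DSMB review.

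- Bullet 1: any dosing-related death.
- Bullet 2: "More than one event comprising systemic allergic symptoms with significant hypotension at any stage of the protocol".
- Bullet 3: "More than 3 participants require more than 2 injections of epinephrine during dosing of the peanut product".
- Bullet 4: more than 3 events drawn from eosinophilic esophagitis and "Severe adverse event, other than anaphylaxis, related to investigational product".

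The section defines neither anaphylaxis nor severe. Appendix 3 is the only place that defines and stages anaphylaxis. Its third stage is headed "Severe (hypoxia, hypotension, or neurological compromise", and its features are cyanosis or SpO2 below 92%, then "at any stage, hypotension, confusion, collapse, loss of consciousness; or incontinence". Unless blood pressure is reduced, Appendix 3 requires involvement of more than one system.

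Reactions to dosing are graded by Table 3 (section 8.4.1.1). Grade 4 there includes "Persistent hypotension and/or hypoxia with resultant decreased level of consciousness". Expected, related symptoms within two hours of a dose go on dosing forms and are not normally recorded as AEs (8.2.2). Section 8.3.2.2 makes exceptions: "Any of the following symptoms or events that occur at any time related to dosing, should also be recorded as an adverse event". The list that follows includes cyanosis, SpO2 below 92%, confusion, collapse and loss of consciousness.

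**The concern.** Bullet 2 shows that the sponsor wants severe anaphylaxis to be able to stop the trial. But bullets 1 to 3 cover only part of what Appendix 3 calls severe. A child with hypoxic anaphylaxis and preserved blood pressure, who recovers after one or two injections, meets none of them, and bullet 4 excludes the event by name.

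Participants are 12 to under 48 months old, and section 1.4.1 names severe anaphylaxis as a risk of dosing. Because it is named there, a serious case would ordinarily be expected under 8.2.5 and go to the annual IND report under 8.5.2. Those who decide under 8.3.2.3 whether a stopping rule has been met would have no rule that counts it. A run of such events could build up while enrollment and escalation continue, unless someone chose to act.

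**Working it through.** The protocol states no event rate and no operating characteristics for these rules, so there is no figure to reproduce. The check is one of definitions, followed by an illustration of what the fix would do.

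**Three test reactions after a dose, all non-fatal and each treated with at most 2 injections**

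| Reaction | Anaphylaxis under Appendix 3? | Bullet 2 | Bullet 3 | Bullet 4 | Events needed to suspend |
|---|---|---|---|---|---|
| A: wheezing with dyspnea, SpO2 90%, no other system | No: one system, blood pressure normal | No | No | Counts, once recorded as a related AE | 4 |
| B: A plus generalized hives | Yes: criterion 1; Stage 3 by SpO2 | No | No | Excluded | None suffices |
| C: B plus significant hypotension | Yes: Stage 3 | Counts | No | Excluded | 2 |

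- Reaction A is a single system because Appendix 3 puts its features under one item: "Airway compromise (e.g., dyspnea, stridor, wheeze/ bronchospasm, hypoxia, reduced PEF". It is Table 3 grade 3 (wheezing with dyspnea), and SpO2 below 92% puts it in the AE record under 8.3.2.2.
- Reaction B is in the AE record for the same reason, so the routing of dosing symptoms to separate forms does not explain the difference. Only the word anaphylaxis does.
- A Table 3 grade 4 reaction reached through hypoxia, if it meets the anaphylaxis criteria and there is no hypotension, follows row B.
- The contrast between A and B holds only for single-system severe reactions that reach the AE record. Wheezing with dyspnea alone, expected, within two hours and without a listed sign, stays on the dosing form.

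**Illustration of the fix**

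Inputs: n = 96 OIT children (section 9.3); threshold of more than 3, so at least 4 (3.4.1); per-child rate p of severe anaphylaxis without hypotension (assumed); one event per child (assumed).

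P(X ≥ 4) = 1 − Σ C(96,k) p^k (1−p)^(96−k), for k = 0 to 3.

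For p = 0.02 the four terms are 0.1438, 0.2817, 0.2731 and 0.1746, which sum to 0.8732, so P(X ≥ 4) = 0.127.

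| Assumed p | Fixed bullet 4, these events alone |
|---|---|
| 1% | 0.016 |
| 2% | 0.127 |
| 3% | 0.325 |
| 5% | 0.713 |
| 10% | 0.989 |

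Under the current rules, non-fatal cases can count only through bullet 3. If a share q of them needs more than 2 injections, replace p by p × q:

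| Assumed p | q = 0% | q = 10% | q = 25% |
|---|---|---|---|
| 5% | 0 | 0.001 | 0.033 |
| 10% | 0 | 0.016 | 0.220 |

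**The case against.** **The threshold may be deliberate.** Anaphylaxis is an expected reaction to OIT, and hypotension is the marker used in exclusion criterion 1, in section 5.2 and in bullet 2. Bullet 3 adds a trigger based on intensity of treatment. This stands as a reason to leave milder anaphylaxis out of bullet 4. It does not explain leaving out hypoxic or neurological cases that the sponsor's own staging calls severe, and the protocol gives no reason for doing so.

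**Section 3.4.1 does not cite Appendix 3.** The appendix says only that anaphylaxis is likely when its criteria are met, so an investigator could call reaction A anaphylaxis too. Alternatively, bullet 4 could be meant mainly for harms other than dosing reactions, in line with 8.2.2. On either reading A also goes uncounted. The contrast between A and B then disappears, but B is still uncounted.

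**These events are not invisible.** A reader might infer that severe anaphylaxis goes unmonitored. The documents do not support that. Serious cases are recorded, and the Medical Monitor, Protocol Chair or co-Chair and trial physician notified, within 24 hours (8.3.2.3). The DSMB receives SAE data on an ongoing basis and reviews them annually (8.5.3). Escalation on the first dosing day is discontinued for severe symptoms (6.7.2). What is missing is an automatic pause.

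**Individual treatment is not shown to be inverted.** A reader might also infer that child A must stop therapy under 5.2 while child B may continue. Section 6.7.3 names wheezing with dyspnea among the severe symptoms after which the physician may continue any child at a reduced dose, so that contrast is not secure.

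**Conclusion.** The gap is real and narrow. Non-fatal anaphylaxis that is severe under Appendix 3 through hypoxia or neurological compromise, without hypotension and treated with 1 or 2 injections, meets no bullet of 3.4.1 at any frequency. This rests on Appendix 3 as the meaning of anaphylaxis and on a literal reading of the bullets. It does not affect the endpoint analyses.

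Two larger statements of size are tempting and should be avoided. One is that six of the seven Stage 3 features have no trigger. Bullets 1 and 3 can be met with any of them, and Appendix 3 itself groups syncope and incontinence with reduced blood pressure. The features clearly outside hypotension are cyanosis, SpO2 below 92% and confusion, and the first two both reflect hypoxia. The other is that all 96 OIT children could have such an event unnoticed by the rules. That is only a logical limit: if all 96 had one and 5% needed more than 2 injections (assumed), the same binomial gives a 71% chance that bullet 3 is met.

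The change is worth making because it is cheap and uses the sponsor's own threshold.

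**What to change.** In 3.4.1 bullet 4, replace *other than anaphylaxis* with *other than anaphylaxis without hypoxia (cyanosis or SpO2 < 92%), confusion, collapse or loss of consciousness*. Dosing-related severe anaphylaxis with any of these signs then counts toward the existing threshold of more than 3. Bullet 2 stays as it is for hypotension. Each named sign is a Stage 3 feature in Appendix 3. Incontinence is left out because it is a poor sign at this age.

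The signs are already recorded as AEs under 8.3.2.2. The added work is to classify each flagged event as anaphylaxis or not. The other cost is a possible pause for DSMB review, at the probabilities shown above; it is a pause and not termination.

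No change to the termination list in 5.2 is proposed. Making every Stage 3 feature a reason to end a child's therapy, including after food challenges, is a clinical trade-off that this gap does not settle.
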